4.1 Dispositions of Subjects and Analysis Sets

Disposition of subjects and analysis sets

The disposition of subjects and analysis sets, subjects per center, inclusion and exclusion criteria, and the status at study termination will be presented using summary statistics.

The number of subjects available per visit will be tabulated.

No inferential assessments will be performed on disposition data.

4.2 Demographics and Other Covariates

Demographic data

Demographic data (age, sex, race, height, weight, body mass index) will be summarized by treatment group to describe the study population.

Medical and surgical history

Relevant past medical history will be collected and listed. Migraine history will be listed separately.

Concomitant medication

Concomitant medication will be coded according to World health organization drug dictionary version March 2018.

Medications will be tabulated by anatomic group (ATC) level 4, and WHO-DD preferred term. The number of entries, as well as the number and percentage of affected subjects will be reported.

Urine Pregnancy test

The proportion of patients with positive or negative pregnancy test results from females with childbearing potential will be tabulated.

Physical examination

All information about physical examination will be listed.

4.3 Performance Analysis

For all tests, a two-sided significance level of 5% ($\alpha = 0.05$) will be applied.

Analysis for the primary performance endpoint will be based on the FAS. Additionally, a sensitivity analysis of the primary endpoint will be performed using the PP.

All statistical tests for secondary performance endpoints are considered exploratory and no adjustment for multiplicity is made.

All secondary endpoints will be evaluated for the performance assessment period and the follow-up period.

The 4-week screening period is defined as Baseline.

4.3.1 Analysis of Primary Performance Variable

Mean change from Baseline in 4-week headache days

The mean change from Baseline (4-week screening period) in 4-week headache days with moderate to severe intensity in 4-week performance assessment period (V3 to V7) will be analyzed as follows:

The primary null hypothesis to be tested is

$H_0: \mu_{\text{active}} = \mu_{\text{placebo}}$ against the alternative

$H_1: \mu_{\text{active}} \neq \mu_{\text{placebo}}$,

where μ is the mean change from Baseline (4-week screening period) in 4-week headache days with moderate to severe intensity in 4-week performance assessment period (V3 to V7).

An analysis of covariance (ANCOVA) with treatment, baseline number of headache days, medication overuse as independent variables will be calculated to test above null hypothesis. Check for the normal distribution of data will be performed.

Normality of data cannot be assumed, if at least one of the following items can be demonstrated on the residuals, as determined when applying the ANCOVA as described above:

- p-value using Shapiro-Wilk test on normality < 0.2 .
- Visual check of the QQ-plot shows: plotted points do not approximately lie on the diagonal line $y = x$.

If normality of data cannot be shown, it can be assumed that the data are approximately normal distributed due to the large sample size, i.e. the results of ANCOVA can be implemented in the group-sequential design.

A group-sequential design with O'Brien & Fleming alpha spending function allows adjustment of alpha using spending function according to the information fraction at the interim analysis

available, so that the overall significance level alpha of 0.05 is considered for evaluation at the final analysis.

ANCOVA model as derived from SAS procedure GENMOD will be applied for final analysis to derive a maximum likelihood estimate of the mean difference between active and control group and the corresponding standard error of the mean difference. These parameter estimates will be used in SAS procedure SEQTEST. The implementation details of group-sequential design with O'Brien & Fleming alpha spending function are described in paper (Yuan, 2009). ANCOVA model as derived from SAS procedure GLM provides an approximate maximum likelihood estimate of the mean difference between active and control group in case of normal distribution or naïve estimates from both the mean difference between active and control group and the corresponding standard error of the mean difference in case of not normal distribution. In interim and subgroup analyses SAS procedure GLM was used and therefore this procedure will additionally be applied for checking purposes.

In addition, the number of 4-week headache days and change from Baseline will be presented by descriptive statistics.

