Sample Sizes (N) Two-Sample Z Test for Mean Difference								
Stage	Fractional N				Ceiling N			
	N	N(Grp 1)	N(Grp 2)	Information	N	N(Grp 1)	N(Grp 2)	Information
1	52.51	26.25	26.25	0.3646	54	27	27	0.3750
2	131.26	65.63	65.63	0.9116	132	66	66	0.9167

14 Data handling and record keeping

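### The final primary test sets a maximum-likelihood standard error against a normal boundary, so its type I error is about 5.6%, not the stated 5%

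*SAP*

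**What the plan says.** SAP 4.3.1 specifies the primary model as follows: "An analysis of covariance (ANCOVA) with treatment, baseline number of headache days, medication overuse as independent variables". The estimator for the last look is given separately: "ANCOVA model as derived from SAS procedure GENMOD will be applied for final analysis to derive a maximum likelihood estimate of the mean difference". Its standard error comes from the same fit, and both are passed on: "These parameter estimates will be used in SAS procedure SEQTEST". The SAP describes GLM as giving an approximate maximum-likelihood estimate and limits it to a supporting role: "In interim and subgroup analyses SAS procedure GLM was used and therefore this procedure will additionally be applied for checking purposes".

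SAP 4.3 sets a two-sided 5% level for all tests. SAP 4.3.1 says the alpha-spending design adjusts alpha "so that the overall significance level alpha of 0.05 is considered for evaluation at the final analysis". In Protocol 13.5 the planned boundaries are one-sided p-values of 0.0003942 at the interim and 0.02487 at the final look. The accompanying sample-size table is headed "Two-Sample Z Test for Mean Difference".

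Neither document states a GENMOD scale option, a degrees-of-freedom correction or a t-based p-value for this test.

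**The concern.** In a normal linear model, maximum likelihood and least squares give the same treatment estimate. They differ only in the residual variance. The maximum-likelihood divisor n ignores the four fitted mean parameters (intercept, treatment, baseline, medication overuse), so its standard error is always the smaller of the two. Comparing the resulting ratio with a normal boundary also ignores the uncertainty in the variance estimate. Both departures are anti-conservative.

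The SAP therefore ranks the two procedures the wrong way round. Under normality the least-squares t-test is the exact one, and it is the one kept as a check. The plan also changes variance estimator between the two stages, because GLM was used at the interim.

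What is at stake is the claim of 5% overall error for the only confirmatory test, and a confidence interval that is slightly too narrow. A borderline result could be significant by GENMOD with SEQTEST and not by the GLM t-test, with the more liberal answer designated primary.

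**Working it through.** **Inputs.** From Protocol 13.5: information fraction 0.40 at stage 1, overall alpha 0.05 two-sided, final N = 132, interim at approximately 50 subjects, efficacy boundaries 0.0003942 and 0.02487 per side. From SAP 4.3.1: ANCOVA with four mean parameters, so residual df = 132 − 4 = 128.

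**1. Reproduce the plan's boundaries.** O'Brien-Fleming-type spending with a = 0.025 per side and t = 0.40:

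- Stage 1: 2·[1 − Φ(z₁₋ₐ/₂/√t)] = 0.000394, so z = 3.357.
- Stage 2, from the bivariate normal with correlation √0.40: p = 0.02487, so z = 1.962.

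Both match the protocol. The information level 0.91156 gives N = 0.91156 × 4 × 36 = 131.26, which also matches. The boundaries are correct; the problem lies in the statistic compared with them.

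**2. Size of the standard-error difference.** SE(ML) = SE(least squares) × √((n−4)/n). At n = 132, √(128/132) = 0.985, so the ML standard error is 1.5% too small.

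**3. Type I error of the final look.** Rejecting when |estimate/SE(ML)| > 1.962 is the same as rejecting when the least-squares |t| > 1.962 × √(128/132) = 1.932.

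| Final test at N = 132 | Two-sided error |
|---|---|
| ML standard error, normal boundary (as written): 2·P(t₁₂₈ > 1.932) | 5.55% |
| Least-squares standard error, normal boundary: 2·P(t₁₂₈ > 1.962) | 5.19% |
| Least-squares t-based p-value against 0.02487 per side: 2 × 0.02487 | 4.97% |

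Of the excess of about 0.58 points, 5.55 − 5.19 = 0.36 comes from the divisor and 5.19 − 4.97 = 0.22 from the normal reference.

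**4. Sensitivity to the number evaluable.** As-written error at the final look: 5.75% at N = 100, 5.68% at 110, 5.61% at 120, 5.55% at 132, 5.49% at 148.

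**5. Both looks together.** Null ANCOVA data with normal errors were simulated, with 600,000 trials per scenario, interim n = 50 or 52 and final n = 132. The Monte Carlo standard error is about 0.03 points.

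| Procedure over both looks | Overall error |
|---|---|
| GLM standard error with z at interim, ML standard error with z at final | 5.59% to 5.60% |
| t-based p-value at interim, ML standard error with z at final | 5.55% to 5.56% |
| ML standard error with z at both looks | 5.64% |
| GLM standard error with z at both looks | 5.24% to 5.25% |
| GLM t-based p-values at both looks | 4.98% to 5.00% |

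**6. Interval width.** The t₁₂₈ quantile for 0.02487 per side is 1.981. The as-written multiplier on the least-squares standard error is 1.932, and 1.932/1.981 = 0.975. The interval is about 2.5% narrower than the t-based one, before any stagewise adjustment.

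**The case against.** The strongest objection is that the SAP never states the GENMOD scale option. The words maximum likelihood qualify the estimate, and implementation details are referred to a methods paper that is not among the documents. With a deviance or Pearson scale, the GENMOD standard error equals the least-squares one and the error falls to about 5.2%. This stands as an assumption to declare. The maximum-likelihood reading is still the more natural one, and even the favourable reading exceeds 5%.

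Second, part of the excess comes from the Z-test design in the protocol and not from GENMOD. This is correct, and it means that changing procedure alone is not enough.

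Third, the effect is small. The conclusion changes only for a GLM p-value between about 0.0497 and 0.0555, and the planned GLM check would make any such disagreement visible. That is true, but the SAP does not say what happens if the two disagree, and it makes the more liberal one primary.

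Fourth, the SAP appeals to large samples. That argument concerns non-normal data, not the variance divisor, and the figures above are already at the planned sample size. It is fair to add that if the day counts are clearly non-normal, neither method is exact and the second decimal should not be pressed.

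Fifth, the change of estimator between stages matters little in itself. The interim boundary spends only 2 × 0.0003942 = 0.0008 two-sided, and SAP 4.6 records that the interim led to no stop or adaptation. The inflation is already 5.55% at the final look alone.

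**Conclusion.** The concern holds. As written, the confirmatory test has a type I error of about 5.6% against a stated 5%, an excess of about 0.6 points. The error is always in the direction of declaring a difference.

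This rests on a maximum-likelihood scale in GENMOD, normal errors, 132 evaluable subjects and two looks only, leaving aside the additional analysis of German subjects. With a deviance or Pearson scale the figure is about 5.2%. It is a point that should be corrected, not one that undermines the trial.

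**What to change.** Rewrite the GENMOD paragraph of SAP 4.3.1 as follows:

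- Make the least-squares ANCOVA (GLM, or REML) the primary analysis, as at the interim. Report the estimate, its standard error on n−4 residual degrees of freedom and the t-based p-value.
- Compare that p-value with the SEQTEST final boundary (planned 0.02487 per side, recomputed at the actual information fraction), or convert it to a z-value before it enters SEQTEST.
- Drop the GENMOD standard error or keep it as the check, stating its scale option.
- State that the least-squares t-based result decides if the two differ.

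Replacing only the standard error is not sufficient; the t-based p-value is what brings the error back to about 5.0%. The change should be made before final unblinding, since choosing between two standard errors afterwards would look driven by the result. The cost is one SAP paragraph and a slightly less favourable p-value, with no effect on data, patients or sample size.

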4.3.2 Analysis of Secondary Performance Variables

The analyses of the secondary performance variables will be performed using the FAS. All statistical tests will be considered exploratory and no adjustment for multiplicity will be made.

Mean change from Baseline in 4-week headache in follow-up period

The mean change from Baseline in 4-week headache days in follow-up period will be similarly analyzed as the primary performance endpoint for the performance assessment period. If the data is normally distributed an ANCOVA will be calculated to test above null hypothesis. If the data is not normally distributed the van Elteren test will be used with medication overuse as stratification to test above null hypothesis.

The analysis for the performance assessment period is covered by the primary analysis.

Mean change from Baseline in 4-week migraine days

The mean change from Baseline in 4-week migraine days will be similarly analyzed as the primary performance endpoint; however, the number of migraine days instead of number of headache days will be counted. If the data is normally distributed an ANCOVA will be calculated to test above null hypothesis. If the data is not normally distributed the van Elteren test will be used with medication overuse as stratification to test above null hypothesis.

Mean change from Baseline in 4-week headache days (mild, moderate and severe intensity) in 4-week performance assessment period (V3 to V7)

The mean change from Baseline in monthly headache days with mild to severe intensity will be similarly analyzed as the primary performance endpoint; however, the number of headache days with mild intensity will be included. If the data is normally distributed an ANCOVA will be calculated to test above null hypothesis. If the data is not normally distributed the van Elteren test will be used with medication overuse as stratification to test above null hypothesis.

Proportion of subjects with 30% or greater reduction in headache days

The proportion of subjects with 30% or greater reduction from baseline period to performance assessment period and to follow-up period will be presented descriptively using frequency tables

summarizing the number and percentage of patients with a headache reduction of 30% or greater.

Additionally, active and placebo treatment arms will be compared using a Chi-square test. In case of less than 5 subjects per group, the Fisher's exact test will be used.

Proportion of subjects with 50% or greater reduction of headache days

The proportion of subjects with 50% or greater reduction from baseline period to performance assessment period and to follow-up period will be presented descriptively using frequency tables summarizing the number and percentage of patients with a headache reduction of 50% or greater.

Additionally, active and placebo treatment arms will be compared using a Chi-square test. In case of less than 5 subjects per group, the Fisher's exact test will be used.

Change in the use of acute (abortive) medication

Information about the use of abortive medication is given in the patient diary. The number of days with abortive medication will be summed up per 4-week period.

The absolute 4-week use of abortive medication and change from Baseline in 4-week use of abortive medication will be presented by descriptive statistics.

Headache impact test-6 (HIT-6)

The total HIT-6 score and change from Baseline will be presented by descriptive statistics. The number and percentage of patients in each category will be presented for each of the 6 items. The total HIT-6 score change from Baseline will be tested using a Wilcoxon rank sum test.

All HIT-6 items must be answered to receive a total HIT-6 score. The total HIT-6 score will be calculated as the weighted sum of answers. The answers are weighted with points as follows:

Answer	Point
Never	6
Rarely	8
Sometime	10
Very often	11
Always	13

Further details of HIT-6 handling are described in user's guide (Bayliss & Batenhorst, 2002).

In tables and listings the HIT-6 items will be labeled as follows:

Question No.	Question Text in CRF	Label for listings and tables
1.	When you have headaches, how often is the pain severe?	Level of severe pain
2.	How often do headaches limit your ability to do usual daily activities including household work, work, school, or social activities?	Activity
3.	When you have a headache, how often do you wish you could lie down?	Tiredness
4.	In the past 4 weeks, how often have you felt too tired to do work or daily activities because of your headaches?	Fatigue
5.	In the past 4 weeks, how often have you felt fed up or irritated because of your headaches?	Psychological distress
6.	In the past 4 weeks, how often did headaches limit your ability to concentrate on work or daily activities?	Cognitive function

Migraine-specific quality of life questionnaire (MSQ)

The 3 dimensions of the MSQ will be presented by descriptive statistics for absolute values and changes from Baseline. The changes from Baseline will be tested using a Wilcoxon rank sum test for each of the 3 dimensions.

The scoring of the MSQ items is completed in 3 steps:

1. Recoding of MSQ items

The MSQ items are worded with a negative perspective, therefore they must be recoded before the domain scores are calculated.

Item Number	Response categories Precoded	Precoded item value	Final item value
1-14	None of the time	1	6
	A little bit of the time	2	5
	Some of the time	3	4
	A good bit of the time	4	3
	Most of the time	5	2
	All of the time	6	1

2. Computation of raw domain scores: the algebraic sum of the final item value for all items in that domain:

Domain	Cluster of Items
Role function - Restrictive	1 - 7
Role function - Preventive	8 - 11
Emotional function	12 - 14

3. Transformation of raw domain scores to a 0 to 100 scale.

Domain	Raw score range	Transformation formula
Role function - Restrictive	7 to 42	(raw score - 7)*100/35
Role function - Preventive	4 to 24	(raw score - 4)*100/20
Emotional function	3 to 18	(raw score - 3)*100/15

Further details of MSQ scaling and scoring as well as handling of missing data are described in manual (Mapi Research Teust, 2017).

Patient global impression of severity (PGI-S)

The score will be presented descriptively using frequency tables. The change from Baseline will be assessed with a shift table of baseline versus post-baseline assessments.

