11.2.3 Methods of assigning subjects to device groups

Subjects will be randomly assigned in a 1:1 ratio to active or placebo treatment by means of a computer-generated randomization list. Randomization will be stratified by medication overuse (yes/no) at V1.

Medication overuse is defined as regular overuse for >3 months of one or more acute symptomatic drugs (according to the IHS classification):

- Ergotamine, triptans, opioids or combination analgesic medications on ≥ 10 days per month on a regular basis for >3 months;
- Simple analgesics or any combination of ergotamine, triptans, analgesics or opioids on ≥ 15 days per month on a regular basis for >3 months without overuse (≥ 10 days) of any single class alone.

The Chordate System S211 can deliver normal (active) treatment or placebo treatment. The user will enter the randomization number assigned to the patient before start of treatment, and based on a hidden randomization table; the controller will either deliver active or placebo treatment.

The controller acts in one of two modes:

- Active treatment: The controller creates air-mediated kinetic oscillations with regulated pressure and frequency during a preset treatment time.
- Placebo treatment: Placebo treatment is similar to active treatment, but with no oscillations.

It is difficult to discern any difference between active and placebo treatment.

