All statistical tests for secondary performance endpoints are considered exploratory and no adjustment for multiplicity is made.

All secondary endpoints will be evaluated for the performance assessment period and the follow-up period.

Mean change from Baseline in monthly headache days with moderate to severe intensity in follow-up period

The mean change from Baseline in monthly headache days in follow-up period will be similarly analyzed as the primary performance endpoint for the performance assessment period. The analysis for the performance assessment period is covered by the primary analysis.

Mean change from Baseline in monthly migraine days

The mean change from Baseline in monthly migraine days will be similarly analyzed as the primary performance endpoint; however, the number of migraine days instead of number of headache days will be counted.

Mean change from Baseline in monthly headache days (mild, moderate and severe intensity) in 4-week performance assessment period (V3 to V7)

The mean change from Baseline in monthly headache days with mild to severe intensity will be similarly analyzed as the primary performance endpoint; however, the number of headache days with mild intensity will be included.

Proportion of subjects with 30% or greater reduction in headache days of moderate to severe intensity

The proportion of subjects with 30% or greater reduction from baseline period to performance assessment period will be presented descriptively using frequency tables.

Additionally, active and placebo treatment arms will be compared using a Chi-square test. In case of a low number of subjects per group, the Fisher's exact test will be used.

Proportion of subjects with 50% or greater reduction of headache days of moderate to severe intensity

The proportion of subjects with 50% or greater reduction from baseline period to performance assessment period will be presented descriptively using frequency tables.

Additionally, active and placebo treatment arms will be compared using a Chi-square test. In case of a low number of subjects per group, the Fisher's exact test will be used.

Change in the use of abortive medication

The change from Baseline in monthly use of abortive medication will be presented by descriptive statistics.

Headache impact test

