13.5 Sample size calculation

For the fixed sample size approach approximately 140 subjects should be enrolled in order to achieve at least 128 subjects evaluable for the primary performance endpoint. If during the conduct of the study the drop-out rate proves to be higher than expected (>10%), enrolment would continue until at least 128 subjects were assessed for the primary endpoint.

The fixed sample size estimation delivered 128 subjects (64 per group) to be sufficient to detect a difference in means between the treatment groups of the primary performance endpoint of 3 days (e.g. by assuming a change in monthly headache days in the placebo group of 2, and in the active group of 5) and assuming that the common standard deviation is 6 using a 2-group t-test with a 0.05 two-sided significance level and a power of 80%.

As one interim analysis with the possibility to stop for efficacy or to stop for (a non-binding) futility shall be introduced, the sample size has to be revisited. An alpha spending function of the O'Brien Fleming type is applied having 2 analysis stages (one interim stage and one final analysis stage). The interim analysis will be performed after approximately 50 subjects (approximately 40% of fixed sample size) have completed the 6-week treatment period (Visit 7) (unequal spaced analyses stages). The final analysis will be performed after N=132 subjects are assessable. With respect to a drop-out rate of 10% 148 patients have to be enrolled.

The calculation of critical values for the interim analysis was performed using SAS 9.4/ PROC SEQDESIGN. A group-sequential design using an O'Brien & Fleming alpha spending function with two stages (information fraction at stage 1 is 40%, an overall significance level alpha of 0.05 and beta of 0.2) has been considered. The table below shows boundaries to be met at the interim and final analysis for claiming efficacy or stop for (non-binding) futility at pre-specified information levels. Actual boundaries will be calculated with respect to the available information fraction levels at each stage of analysis.

Boundary Information (p-Value Scale) Nonbinding Beta Boundary, Null Reference = 0									
Stage	Information Level			Alternative		Boundary Values			
	Proportion	Actual	N	Reference	Lower	Upper	Beta	Beta	Alpha
1	0.4000	0.364624	52.50584	-1.81152	1.81152	0.0003942	0.39397	0.60603	0.99961
2	1.0000	0.91156	131.2646	-2.86427	2.86427	0.02487	0.02487	0.97513	0.97513

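### The 30% and 50% responder comparisons ignore the randomisation stratum, which makes them valid but somewhat conservative; the Fisher trigger is ambiguous but causes no material error

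*SAP*

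**What the plan says.** Protocol 11.2.3 names one stratification factor: "Randomization will be stratified by medication overuse (yes/no) at V1". The SAP then uses it. The primary ANCOVA (SAP 4.3.1) has medication overuse as a covariate. The headache-day and migraine-day secondary endpoints (SAP 4.3.2) are analysed like the primary endpoint, or by a van Elteren test stratified by medication overuse if the data are not normal.

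The two responder endpoints are handled differently. For both the 30% and the 50% threshold, SAP 4.3.2 says that "active and placebo treatment arms will be compared using a Chi-square test. In case of less than 5 subjects per group", Fisher's exact test is used instead. No stratum or covariate is named. Protocol 13.2 has the same pair of tests with a vaguer switch, "In case of a low number of subjects per group". The SAP asks for counts and percentages by arm. In the text available it names no between-arm difference or confidence interval. Responder rate is listed in the secondary objectives (Protocol 10), and all secondary tests are declared exploratory without multiplicity adjustment.

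**The concern.** When arms are balanced within strata by design, differences in response between strata no longer contribute to the error of the treatment comparison. An unstratified chi-square test still counts them as noise. Its standard error is therefore too large, its type I error falls below 5%, and it loses power. How much depends on how strongly medication overuse predicts response. The plan already accepts this logic for the day counts from which responders are derived.

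The second issue is the Fisher switch. Whether the chi-square approximation is adequate depends on expected cell counts, not on the number of subjects in an arm. If subjects per group means arm size, the switch is dead text. If it means responders per group, it is a working rule, though on observed rather than expected counts. The two readings can select different tests for the same table, and the choice could be made after the counts are known.

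**Working it through.** **Arm size.** Protocol 13.5 plans for a "difference in means between the treatment groups of the primary performance endpoint of 3 days", "assuming that the common standard deviation is 6", with two-sided alpha 0.05 and 80% power.
- Fixed design, normal approximation: n per arm = 2 × (1.96 + 0.8416)² × 6² / 3² = 62.8, so 63. The exact t-test gives 63.8, so 64 per arm, as stated.
- Group-sequential design: the tabulated drift 2.86427 gives N = (2.86427/3)² × 4 × 6² = 131.26, rounded up to 132, or 66 per arm, as stated.

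The responder tables are therefore taken as 66 per arm.

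**Effect of ignoring the stratum.** The documents give neither responder rates by stratum nor the share with medication overuse. Both are assumptions here: two equal strata (33 per arm in each) and four pairs of placebo rates. For stratum rates a and b with mean p, the chi-square test uses variance T = p(1−p). The variance that applies with balanced strata is W = [a(1−a) + b(1−b)]/2. The effective critical value is 1.96/√(W/T). For 10%/40%:
- T = 0.25 × 0.75 = 0.1875
- W = (0.09 + 0.24)/2 = 0.165
- W/T = 0.88, and 1.96/0.938 = 2.089, a two-sided error of 3.7%

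Simulation (200,000 trials per scenario) agrees closely with the formula:

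| Placebo rates | W/T | Formula error | Chi-square error | CMH error | Power at +20 points, chi-square v CMH |
|---|---|---|---|---|---|
| 25%/35% | 0.988 | 4.9% | 4.85% | 4.96% | 65.5% v 65.7% |
| 15%/35% | 0.947 | 4.4% | 4.35% | 4.99% | 69.1% v 70.2% |
| 20%/50% | 0.901 | 3.9% | 4.04% | 4.93% | 63.3% v 68.8% |
| 10%/40% | 0.880 | 3.7% | 3.62% | 5.00% | 69.7% v 72.6% |

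The power loss runs from 0.2 to 5.5 points. A wider grid (overuse share 30% to 70%, common odds ratio 2.7) gave almost no loss when the strata had equal rates. The loss reached about 12 points only in an extreme case: placebo rates of 5% with overuse and 40% without, and 70% overuse.

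**Fisher switch.** At 66 per arm, an arm with fewer than 5 subjects cannot occur. An expected responder count below 5 needs a pooled responder rate below 5/66 = 7.6% (by symmetry, above 92.4%). Exact enumeration of type I error at 66 per arm:

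| Responder rate | Chi-square | Fisher |
|---|---|---|
| 2% | 2.3% | 0.1% |
| 5% | 4.7% | 1.2% |
| 7.6% | 5.1% | 1.9% |
| 10% | 5.1% | 2.4% |
| 20% | 4.9% | 3.1% |

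The largest chi-square error in the sparse region (below 7.6%) is 5.1%.

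Two tables show what the ambiguity can do. With 0 v 4 responders of 66, z = (4/66)/√(0.0303 × 0.9697 × 2/66) = 2.03, so chi-square p = 0.042; Fisher p = 0.119. With 4 v 12, where 8 are expected per arm, z = 2.13, so chi-square p = 0.033; Fisher p = 0.059. In each table, reading the rule as arm size selects chi-square and reading it as responders selects Fisher, on opposite sides of 0.05.

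**The case against.** A reader might infer that the plan uses the wrong test exactly when counts are small. The documents do not support that. The switch can be read as fewer than 5 responders per group, in which case Fisher is used for small counts. Read as arm size, it leaves chi-square in place, and chi-square holds its level in sparse tables of this size. The 0 v 4 table shows that Fisher is more conservative, not that chi-square is invalid. Sparse tables also need pooled rates under 7.6%, which nothing in the documents predicts. What stands is an ambiguity, not an error.

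A reader might also infer that no effect is reported. Counts and percentages by arm are planned, so the difference can be obtained by subtraction. Only an interval is unmentioned, and Appendix A of the SAP, which holds the output details, is not available to settle it.

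On stratification, the fair reply is that this is a matter of efficiency. The error rate stays below 5%, and the larger power gains need medication overuse to shift response by about 30 points, which is unsupported. The tests are exploratory, and Protocol 13.3 does not list responder rates among the secondary endpoints considered for futility. All of that stands. It limits the importance of the point but gives no reason to drop the stratum here while keeping it for the underlying day counts.

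**Conclusion.** The responder comparisons are inconsistent with the stratified randomisation and with the SAP's own handling of the day counts. The consequence is lost precision, not bias: type I error about 4.9% to 3.6% instead of about 5%, and a power loss of about 0 to 6 points for a 20-point difference. Those figures rest on 66 per arm, equal strata and assumed placebo rates from 25%/35% to 10%/40%. If overuse does not predict response, the loss is practically nil. The Fisher wording needs clarifying because the two readings can give different p-values, but it causes no material inflation of error. Neither matter affects the primary conclusion. This is a free improvement rather than a correction of an invalid analysis.

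**What to change.** In SAP 4.3.2, for the 30% and 50% responder endpoints and for both the performance assessment and follow-up periods, replace the chi-square/Fisher rule with a CMH test stratified by medication overuse. Report the stratified risk difference with its 95% CI.

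If an exact fallback is kept, define it on the expected counts summed over strata (the pooled table, any below 5), not on each stratum table. In a check with 33 per arm per stratum (40,000 runs), a per-stratum trigger fired under the null in 46% of trials at 15%/35% and 88% at 10%/40%. Type I error was then 3.9% and 3.3%, below the 4.2% and 3.7% of the plain chi-square test in the same runs.

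Keep the tests labelled exploratory. Make the change before final unblinding; after that, report the stratified result as a labelled supplementary analysis. The cost is a few lines of SAP wording and a programming option in the software already used, with no new data and no additional subjects.
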